### 9.5.1.9.1 Health Assessment Questionnaire – Disability Index

The HAQ-DI, which is part of the SHAQ (Section 9.5.1.9.4), assesses the subject's level of functional ability and includes questions of fine movements of the upper extremity, locomotor activities of the lower extremity and activities that involve both upper and lower extremities. There are 20 questions in 8 categories of functioning including dressing, rising, eating, walking, hygiene, reach, grip and usual activities [Cole et al., 2006]. The subject's ability to accomplish each activity in the past week is indicated as: without any difficulty, with some difficulty, with much difficulty and unable to do. Any devices that are usually used to complete activities and any categories for which help from another person is needed is also assessed.

In addition, the subject will be asked the following anchor (additional) questions at the time points specified in Section 2.1.

How did your systemic sclerosis limit your daily activities in the last week?

- 0: did not limit activity
- 1: mildly limited my activity
- 2: moderately limited my activity
- 3: severely limited my activity
- 4: very severely limited my activity

How has limitation of your daily activities changed since the start of the trial?

- +3: very much less limited
- +2: much less limited
- +1: a little less limited
- 0: no change
- -1: a little more limited
- -2: much more limited
- -3: very much more limited

### 9.5.1.9.2 Patient Global Assessment

The PTGA is an 11-point Likert scale ranging from 0 to 10 (0=excellent to 10=extremely poor) on which the subject rates his/her overall health and illness-related pain level over the past week and how much the skin involvement due to scleroderma has interfered with daily activity and how rapidly the skin disease has been progressing over the past month. There is also a 5-point Likert scale (from 1 to 5; 1=much better to 5=much worse) on which the subject rates overall scleroderma skin involvement compared to the last clinic visit.

### 9.5.1.9.3 Scleroderma Skin Patient-reported Outcome Instrument

The SSPRO-18, developed through concept elicitation in patients with diffuse cutaneous and limited cutaneous SSC based on 3 focus groups, is an 18-item, patient-reported outcome

instrument that specifically assesses skin-related quality of life in patients with SSc and was developed with extensive patient input and according to the FDA patient-reported outcomes guidance [Man et al., 2017]. The SSPRO-18 comprises 4 major conceptual constructs—physical effects, emotional effects, physical limitations and social effects—and has reproducibility and high internal consistency. This instrument reflects how subjects feel and function from several different health perspectives. Good test-retest reliability and construct validity has been shown [Man et al., 2017]. Responsiveness has been shown for lenabasum vs placebo [Spiera et al., 2020].

In addition, the subject will be asked the following anchor (additional) questions at the time points indicated in Section 2.1.

How severely was your skin affected by systemic sclerosis in the last week?

- 0: My skin was not affected by systemic sclerosis.
- 1: My skin was mildly affected by systemic sclerosis.
- 2: My skin was moderately affected by systemic sclerosis.
- 3: My skin was severely affected by systemic sclerosis.
- 4: My skin was very severely affected by systemic sclerosis.

How much did your skin's tightness limit your daily activities in the last week?

- 0: skin tightness did not limit activity
- 1: skin tightness mildly limited my activity
- 2: skin tightness moderately limited my activity
- 3: skin tightness severely limited my activity
- 4: skin tightness very severely limited my activity

How has your skin changed since the start of the trial?

- +3: very much better
- +2: much better
- +1: a little better
- 0: no change
- -1: a little worse
- -2: much worse
- -3: very much worse

#### 9.5.1.9.4 Scleroderma Health Assessment Questionnaire

The SHAQ consists of the HAQ-DI (8 domains) and also includes a VAS for pain and the following scleroderma-specific VASs: patient global assessment, vascular, digital ulcers, lung involvement and gastrointestinal involvement [Steen and Medsger, 1997]. Developers added the global questions to the HAQ-DI based on evaluation of SSc patients at the University of

Pittsburgh Scleroderma Clinic, their HAQ scores, patient report of symptoms and lab tests. The 5 scleroderma-specific VASs ask subjects how much symptoms interfere with daily activities and are scored similarly to a pain VAS. Each VAS score is reported individually. Studies have supported excellent test-retest reliability and construct validity (correlation with other measures in the direction and to the magnitude expected) and responsiveness of abatacept vs placebo for the global questions from the SHAQ [Johnson et al., 2005; Smyth et al., 2003; Khanna et al., 2020].

### **9.5.1.9.5 UCLA Scleroderma Clinical Trial Consortium Gastrointestinal Tract Instrument**

The UCLA SCTC GIT 2.0 captures SSc-related gastrointestinal activity and severity. This instrument is an improvement over the scleroderma gastrointestinal tract (SSC-GIT 1.0) instrument because it is shorter (34 items versus 52 items) but still reliable and valid instrument that differentiates reflux symptoms from symptoms of distension/bloating, adds a scale to evaluate rectal incontinence because of its high prevalence in SSc and develops a composite score that captures overall gastrointestinal tract burden associated with SSc [Khanna et al., 2009].

The UCLA SCTC GIT 2.0 has 7 scales—reflux, distension/bloating, diarrhea, fecal soilage, constipation, emotional well-being and social functioning; a total GIT score is also calculated to capture overall burden of SSc-associated gastrointestinal involvement. Items are scored on a 0 to 3 scale and do not require conversion to a 0 to 100 scale.

### **9.5.1.9.6 Raynaud's Assessment**

The Raynaud's Condition Score Diary captures frequency, duration and severity of Raynaud's phenomenon activity and has face, content, criterion, discriminant and construct validity in subjects with SSc [Merkel et al., 2003]. Subjects will be provided an electronic device to capture symptoms.

## **9.5.1.10 Health Status and Systemic Sclerosis-specific Quality of Life Measures**

A copy of each assessment is provided in the Appendix (Section 17).

### **9.5.1.10.1 Systemic Sclerosis Quality of Life Questionnaire**

The SScQoL, developed through concept elicitation interviews in patients with diffuse cutaneous and limited cutaneous SSc, is a validated tool that has 29 questions divided into 5 subscales relating to physical functioning, emotional functioning, social functioning, sleep and pain, which are important disease-specific factors associated with quality of life in SSc [Sierakowska et al., 2019]. Good test-retest reliability and construct validity has been shown [Reay 2008]. No studies have yet determined responsiveness to date.

### **9.5.1.10.2 SF-12 Health Survey**

The SF-12 [Ware et al., 1996] is a 12-item survey used to assess general health-related quality of life. The SF-12 items are scored to generate a physical component score (PCS) and mental component score (MCS) from the subject's perspective. The SF-12 examines 8 domains of health outcomes, including physical functioning, role-physical, bodily pain, general health, vitality, social functioning, role-emotional and mental health.

### **9.5.1.10.3 Pain Questionnaire**

Subjects will complete a pain questionnaire that has 3 questions regarding the severity of pain experienced during the past week due to Raynaud's, arthritis and finger ulceration and/or calcinosis. Subjects will rate their pain from 0 (no pain) to 10 (very severe pain).

### **9.5.1.10.4 Functional Assessment of Chronic Illness Therapy – Fatigue Scale**

The FACIT-F is a 13-item measure that assesses self-reported fatigue and its impact upon daily activities and function. It was developed in the mid-1990s to meet a growing demand for more precise evaluation of fatigue associated with anemia in cancer patients. Subsequent to its development, it has been employed in over 150 published studies, including over 40,000 patients. Studied groups have included patients with cancer, rheumatoid arthritis, osteoarthritis, psoriatic arthritis, ankylosing spondylitis, multiple sclerosis, psoriasis and SSc. The FACIT-F is reliable and valid in subjects with SSc [Harel et al., 2012; Strickland et al., 2012].

## **9.5.2 Pharmacokinetic Measurements**

Blood samples will be collected from all subjects to evaluate the PK of fipaxalparant (HZN-825) at each of the following visits: Day 1 (pre-dose), Week 4 (pre-dose and 2 to 4 hours post-dose) and Weeks 16, 28 and 40 (pre-dose only at these 3 visits). For the Week 4 Visit (the only visit with post-dose PK samples), the morning dose regimen will be taken in the clinic. All pre-dose samples will be collected prior to any fipaxalparant (HZN-825) administration for the day. PK sample collection time and the most recent dosing time prior to PK sample collection will be recorded for all PK samples.

If the clinic visit is in the morning, on days when a pre-dose PK sample will be collected (i.e., Day 1 and Weeks 4, 16, 28 and 40), subjects will be instructed to withhold taking fipaxalparant (HZN-825) before the visit, and fipaxalparant (HZN-825) and a meal will be administered in the clinic after the pre-dose PK samples are taken. Time of fipaxalparant (HZN-825) administration in the clinic as well as the most recent dosing time prior to the visit will be recorded; 1 additional PK sample will be collected 2 to 4 hours after dosing in the clinic for during the Week 4 Visit.

If the clinic visit is in the afternoon, on days when a pre-dose PK sample will be collected (i.e., Day 1 and Weeks 4, 16, 28 and 40), subjects will be instructed to take fipaxalparant (HZN-825) before 8 a.m. with a meal and record dosing time; 1 PK sample will be

collected anytime during the clinic. For the Week 4 Visit, subjects will receive the evening dose during the visit (dosing time to be recorded) if it is at least 8 hours from the morning dosing and an additional PK sample will be collected 2 to 4 hours post-dose during this visit. At Weeks 16, 28 and 40, subjects will be instructed to take the evening dose at regular dosing time.

Instructions for collection, processing, handling, storing and shipping of PK samples will be detailed in a laboratory manual that will be provided to each site prior to site initiation.

### **9.5.3 Safety Variables**

Safety will be assessed via AEs, concomitant medication use, physical examination, vital signs, [REDACTED] assessment, laboratory evaluations and 12-lead ECG.

#### **9.5.3.1 Adverse Events**

##### **9.5.3.1.1 Definitions**

###### **9.5.3.1.1.1 Adverse Event Definition**

According to ICH, an AE is any untoward medical occurrence in a patient or clinical investigation subject administered a pharmaceutical product and which does not necessarily have a causal relationship with this treatment. An AE can therefore be any unfavorable and unintended sign (including an abnormal laboratory finding), symptom or disease temporally associated with the use of a medicinal (investigational) product, whether or not considered related to the medicinal (investigational) product.

A suspected adverse reaction means any AE for which there is a reasonable possibility that the drug caused the AE. Reasonable possibility means there is evidence to suggest a causal relationship between the drug and the AE.

Exacerbation of a chronic or intermittent pre-existing condition that worsens in intensity or increases in frequency during a trial is to be reported as an AE.

Unchanged, chronic conditions are **NOT** considered AEs and should not be recorded on the AE pages of the eCRF unless there is a clear exacerbation of a chronic condition.

Disease progression can be considered as a worsening of a subject's condition attributable to the disease for which the trial drug is being studied (i.e., SSc). It may be an increase in the severity of the disease under study and/or increases in the symptoms of the disease. Events that are unequivocally due to disease progression should only be reported as AEs if they fulfill any of the SAE criteria or are the reason for discontinuation of trial drug.

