16. Blood samples will be collected for serum and plasma biomarkers prior to dosing on Day [REDACTED] as well as at the [REDACTED] Visit.
17. Adverse events occurring or worsening after the first dose of fipaxalparant (HZN-825) on Day 1 through the Safety Follow-up Visit will be considered treatment-emergent adverse events for this trial. All adverse events that occur from the signing of informed consent through the Safety Follow-up Visit will be recorded. The subject should be assessed for the development of new onset of scleroderma renal crisis, new onset of left ventricular failure, new onset of pulmonary arterial hypertension or right heart catheterization requiring treatment, gastrointestinal dysmotility requiring enteral (tube feeding) or parenteral nutrition or digital ischemia with gangrene, amputation or hospitalization requiring treatment.
18. Includes recording of herb/supplement use. See [Table 9.1](#) for restrictions regarding medications.

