### **9.5.1.4 American College of Rheumatology-Composite Response Index in Systemic Sclerosis**

Subjects will be evaluated using the ACR-CRISS, an outcome measure for diffuse cutaneous SSc. The ACR-CRISS includes core items that assess change in 2 prominent manifestations of early diffuse cutaneous SSc (skin and interstitial lung disease [ILD]), functional disability (HAQ-DI) and patient and clinician global assessments. In addition, the score captures a clinically meaningful worsening of internal organ involvement requiring treatment.

The ACR-CRISS is a 2-step process that assigns a probability of improvement for a subject that ranges from 0.0 (no improvement) to 1.0 (marked improvement). Step 1 will be evaluated as part of the AE assessment, at which time the Investigator will assess if a subject has developed new or worsening cardiopulmonary and/or renal involvement due to SSc, as outlined below.

- New scleroderma renal crisis, defined as follows (adapted from [Steen et al., 2003](#)):  
[Hypertensive scleroderma renal crisis](#):
  1. New onset hypertension, defined as any of the following:
    - a. systolic blood pressure  $\geq 140$  mmHg
    - b. diastolic blood pressure  $\geq 90$  mmHg
    - c. rise in systolic blood pressure  $\geq 30$  mmHg

d. rise in diastolic blood pressure  $\geq 20$  mmHg

AND

2. One of the following 5 features:

- increase in serum creatinine by  $\geq 50\%$  over Baseline OR serum creatinine  $\geq 120\%$  of ULN for local laboratory
- proteinuria  $\geq 2+$  by dipstick
- hematuria  $\geq 2+$  by dipstick or  $\geq 10$  red blood cells/high-powered field
- thrombocytopenia:  $<100,000$  platelets/mm $^3$
- hemolysis, defined as anemia not due to other causes and either of the following:
  - schistocytes or other red blood cell fragments seen on blood smear
  - increased reticulocyte count

Normotensive scleroderma renal crisis:

1. Increase in serum creatinine  $>50\%$  over Baseline OR serum creatinine  $\geq 120\%$  of ULN for local laboratory:

AND

2. One of the following 5 features:

- proteinuria  $\geq 2+$  by dipstick
- hematuria  $\geq 2+$  by dipstick or  $\geq 10$  red blood cells/high-powered field
- thrombocytopenia:  $<100,000$  platelets/mm $^3$
- hemolysis, defined as anemia not due to other causes and either of the following:
  - schistocytes or other red blood cell fragments seen on blood smear
  - increased reticulocyte count

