- Renal biopsy findings consistent with scleroderma renal crisis (microangiopathy)

- Decline in FVC % predicted  $\geq 15\%$  (relative), confirmed by another FVC % within a month, HRCT to confirm ILD (if previous scan did not show ILD) and FVC % predicted  $<80\%$
- New onset of left ventricular failure (defined as ejection fraction  $\leq 45\%$ ) requiring treatment
- New onset of PAH on right heart catheterization requiring treatment
- Gastrointestinal dysmotility requiring enteral (tube feeding) or parenteral nutrition
- Digital ischemia with gangrene, amputation or hospitalization requiring treatment

If a subject meets any of these criteria, the subject is assigned a probability of 0. Otherwise, in Step 2, the probability of improvement is calculated based on the 5 core measures incorporated into the ACR-CRISS, including changes in mRSS, FVC % predicted, HAQ-DI, PTGA and CGA [Khanna and Berrocal et al., 2016].

In addition, the subject will be asked the following ACR-CRISS anchor (additional) questions at the time points indicated in Section 2.1.

Rate the severity of your systemic sclerosis in the last week:

- 0: none
- 1: mild
- 2: moderate
- 3: severe
- 4: very severe

Rate the change in your overall health since you started the trial.

- +3: very much better
- +2: much better
- +1: a little better
- 0: no change
- -1: a little worse
- -2: much worse
- -3: very much worse

Rate the change in your systemic sclerosis since you started the trial.

- +3: very much better
- +2: much better
- +1: a little better
- 0: no change
- -1: a little worse
- -2: much worse
- -3: very much worse

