Events for which the investigator did not record relationship to trial drug will be considered related to trial drug for summary purposes. However, by-subject data listings will show the relationship as missing. No imputation will be done in case of missing study treatment relationship for non-treatment emergent AEs.

The severity grade of events for which the investigator did not record severity will be categorized as “missing” for tabular summaries and data listings. The missing category will be listed last in summary presentation.

Treatment-emergent AEs will be summarized based on the Safety Analysis Set.

Summaries of the following types will be presented:

The number and percentage of subjects who experienced at least 1 TEAE will be provided and summarized by SOC, PT, and treatment group.

The following AEs summaries will be provided by SOC, PT, and treatment group. AE summaries followed by an asterisk(\*) will include the number of events and the corresponding incidence of events per PYE.:

- All TEAEs by maximum severity
- All treatment-emergent SAEs\*
- All treatment-related TEAEs\*
- All treatment-related TEAEs by maximum severity
- All treatment-related treatment-emergent SAEs
- All TEAEs meeting CRISS criteria
- All TEAEs leading to permanent withdrawal of any trial drug
- All TEAEs leading to death (ie, outcome of death)
- All follow-up adverse events
- All serious follow-up adverse events
- Subject incidence of AESIs: [REDACTED]

A brief, high-level summary of AEs described above will be provided by treatment group for the study treatment period and by the number and percentage of subjects who experienced the above AEs. All deaths observed in the trial will also be included in this summary. For the overall summary, the category of “TEAEs by maximum severity” described above will be replaced by AEs with severity > Grade 3.

The frequency of TEAEs occurring in > 5% of subjects in any treatment group will be summarized by treatment, primary SOC, and preferred term. A similar summary will be created for serious TEAEs occurring in > 3% of subjects in any treatment group by primary SOC and preferred term.

An adverse event plot will be created with AE incidences and risk differences (with corresponding exact 95% confidence interval) plotted together for the adverse events occurring in >5% of subjects in any treatment group. A similar plot will be created for SAEs occurring in > 3% of subjects in any treatment group.

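### A CRISS Step 1 organ event that is non-serious and does not stop treatment has no stated route into the responder derivation, because Step 1 is assessed with AEs and the AE definition leaves such progression out.

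*Protocol*

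**What the plan says.** Protocol 9.5.1.4 sets the timing and the assessor: "Step 1 will be evaluated as part of the AE assessment, at which time the Investigator will assess" whether new or worsening involvement due to systemic sclerosis has developed. Six event types count: scleroderma renal crisis, a qualifying FVC decline, left ventricular failure, PAH, gastrointestinal dysmotility needing nutritional support, and digital ischemia. Any one sets the ACR-CRISS probability to 0. Protocol 9.5.1.5 uses the same Step 1 for CRISS 25 and treats the subject as not improved.

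Protocol 9.5.3.1.1.1 describes disease progression as worsening attributable to the disease under study and says: "Events that are unequivocally due to disease progression should only be reported as AEs if they fulfill any of the SAE criteria". It allows one other exception, for progression events that led the subject to stop treatment: "or are the reason for discontinuation of trial drug". The same section also says that exacerbation of a pre-existing "condition that worsens in intensity or increases in frequency during a trial is to be reported as an AE".

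Footnote 17 of the Schedule of Assessments (Protocol 2.1), attached to the AE row, directs sites to look for five of the six event types. It leaves out the FVC decline, and it gives the PAH item as "new onset of pulmonary arterial hypertension or right heart catheterization requiring treatment", where 9.5.1.4 requires PAH *on* right heart catheterization.

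SAP 9.2.7 says that Step 1 events will be adjudicated but does not say from which records. The one SAP output that identifies these events is "All TEAEs meeting CRISS criteria" (SAP 10.3.1).

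**The concern.** Step 1 events are due to systemic sclerosis by definition, so they are the kind of event that the progression rule addresses. A site that follows the AE definition literally would leave off the AE page a Step 1 event that is unequivocally progression, meets no SAE criterion and does not stop the drug. No sentence exempts Step 1 events from that rule, and none names another record for them.

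If such an event is missed, a forced 0 becomes whatever Step 2 returns. The error has one direction: it can turn a non-responder into a responder, never the reverse.

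**Working it through.** The documents give no Step 1 incidence and no responder-rate assumption, so there is no plan figure to reproduce. The check has three parts.

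**1. Is there a stated route for the exposed event?** Take a Step 1 event that is non-serious and does not lead to discontinuation.
- AE page: excluded by 9.5.3.1.1.1 if unequivocally progression. The exacerbation sentence in the same section points the other way, so the section is at best inconsistent.
- Footnote 17: requires assessment of five event types. It requires all AEs to be recorded, but what counts as a reportable AE goes back to 9.5.3.1.1.1.
- Adjudication (SAP 9.2.7): source records not named.
- Spirometry: centrally reviewed at Weeks 16, 28, 40 and 52, independently of AE reporting. The FVC criterion must be "confirmed by another FVC % within a month", and scheduled tests are 12 weeks apart, so scheduled data alone cannot confirm it.
- Echocardiography: scheduled on Day 1 only, then if clinically indicated, so later left ventricular failure cannot be recovered from scheduled data.

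**2. Can Step 2 then return a responder?** SAP 9.2.7 gives P = exp(x)/(1 + exp(x)), with

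x = −5.54 − 0.81·ΔmRSS + 0.21·ΔFVC% − 0.40·ΔPTGA − 0.44·ΔMDGA − 3.41·ΔHAQ-DI.

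A responder needs P ≥ 0.6, that is x ≥ ln(0.6/0.4) = 0.405.
- Only mRSS changes: the fall must be at least (5.54 + 0.405)/0.81 = 7.34 points.
- mRSS −8, nothing else: x = −5.54 + 6.48 = 0.94, P = 0.72.
- mRSS −6, PTGA −1, MDGA −1, HAQ-DI −0.25: x = −5.54 + 4.86 + 0.40 + 0.44 + 0.8525 = 1.0125, P = 0.73.

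Both are responders if a non-FVC organ event goes unrecorded, and 0 if it is recorded. Renal, cardiac, PAH, gastrointestinal and digital events do not enter the equation directly.

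A large FVC fall does not rule out a high Step 2 value. For FVC % predicted 75 to 63.75 (15% relative, Δ = −11.25) and mRSS −11: x = −5.54 + 8.91 − 2.3625 = 1.0075, P = 0.73. This does not show that the true value is 0; see the objection.

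CRISS 25 needs improvement in at least two components and tolerates one worsened component, so the same misclassification is possible there.

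**3. How much could the responder rate move?** Inflation = Step 1 incidence × share unrecorded × share of those passing Step 2. None of these is in the documents. Assumed ranges of 2–10%, 25–100% and 10–50% give:
- low: 0.02 × 0.25 × 0.10 = 0.05 percentage points
- middle: 0.05 × 0.50 × 0.30 = 0.75 percentage points
- high: 0.10 × 1.00 × 0.50 = 5.0 percentage points

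If the eCRF already captures Step 1 separately and completely, the inflation is zero.

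**The case against.** The strongest reply is that "Step 1 will be evaluated as part of the AE assessment" fixes when Step 1 is assessed, not where it is recorded. The eCRF cited by the SAP is not among the documents and may hold a dedicated Step 1 field. Footnote 17 prompts for most of the events, and the SAP plans adjudication and a CRISS table, so the analysis expects these events to be found. This stands as a limit on confidence. It does not supply the missing instruction.

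The exposed group is also narrow. The SAE definition includes medically important events that may need intervention, and four of the six Step 1 criteria involve treatment, nutritional support, amputation or hospitalization. Appendix 17.13 lists scleroderma renal crisis, ventricular failure, PAH, decreased FVC and gangrene among anticipated SAEs. Many Step 1 events would therefore be reported. Its remark that some listed events are serious only at severe intensity gives nausea and vomiting as the example, and neither is a Step 1 event. Deterioration that leads to rescue therapy also prompts (S)AE detail under 9.4.9. All of this stands.

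A reader might infer that Step 1 rests only on spontaneous AE reports, or that the responder rates are inflated. The documents show a possible route to inflation, not that it occurs or how often. A reader might also take the 75-to-63.75 subject as a proven misclassification. That does not follow: besides an FVC below 80% predicted, the criterion needs confirmation within a month and HRCT confirmation of ILD if a previous scan did not show it. Finally, the *or* in footnote 17, read literally, widens capture rather than narrowing it. It is a discrepancy to correct, not a source of the upward bias.

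**Conclusion.** The point holds in a limited form. The two protocol sections conflict for Step 1 events that are unequivocally progression, non-serious and not the reason for stopping drug, and neither document states how those events reach the responder derivation. Any loss raises the ACR-CRISS and CRISS 25 responder rates.

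The size is unknown. The range of 0.05 to 5.0 percentage points rests wholly on assumed inputs, and the true figure may be zero. These endpoints are exploratory, and SAP Section 9 describes its comparisons and p-values as descriptive. The primary FVC endpoint is not affected. The gap is worth closing because the repair is small and the bias has one direction.

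Two wider conclusions are not supported. The AE definition itself need not change: widening it for an efficacy composite would put non-serious progression into the TEAE tables that serve the primary safety objective. Nor does this conflict show that Step 1 events from Trial 301 must be carried into the HZN-825 Baseline analysis. That is a separate question, and it depends on records not provided.

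**What to change.** 1. In Protocol 9.5.1.4 and SAP 9.2.7, state that every Step 1 event is recorded as a CRISS event and sent to the planned adjudication, whether or not it is reportable as an AE, and name the source records. Leave 9.5.3.1.1.1 and the TEAE tables unchanged. The SAP has no CRISS 25 section, so any that is added should refer to the same rule.
2. Align footnote 17 (Protocol 2.1 and the SAP appendix) with 9.5.1.4: add the FVC criterion and reconcile the PAH wording.
3. In the SAP, screen the collected spirometry and central laboratory data for potential Step 1 events and refer hits to adjudication. State that a hit alone does not establish an event; for FVC, the confirmation, ILD and below-80% conditions must also be met.

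The cost is a few sentences in each document and one programmed screen of data already collected. The downside is some additional adjudication referrals, some of them false positives, and possibly slightly lower responder rates. The screen will not find events without scheduled data, such as later left ventricular failure, so item 1 is the essential change.
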